5.4.3 Geometric Mean Ratio

The geometric mean ratio (GMR) is the ratio of two different geometric means (Section Error! Reference source not found.). The GMR and corresponding 95% CI will be calculated using an analysis of variance model (ANOVA). The difference between the natural logarithm of the values and 95% CI will be calculated, with the exponential of these values being the GMR and corresponding 95% CI.

5.4.4 Geometric Mean Fold Rise

The geometric mean fold rise (GMFR) is given by taking the mean of the natural logarithm of the fold increases (**Section 5.3.2.1**). Therefore for the fold increases fi_1, \dots, fi_n , the GMFR is

$$GMFR = \exp \sum_{j=1}^n (\log\{fi_j\} / n).$$

Which is equivalent to

$$GMFR = \frac{GM_4}{GM_2}$$

where GM_2 is the geometric mean at Visit 2 and GM_4 is the geometric mean at Visit 4.

The 95% confidence interval for GMFR will be calculated using the same method as the 95% CI for GM (outlined in **Section 5.4.2**) but using the log of the fold rises rather than the log of concentrations.

6 Sample Size

This trial is designed to be descriptive, and therefore the sample size was not determined based on formal statistical power calculations. The planned number of subjects is approximately 400, with 200 receiving HIL-214 and routine childhood vaccines and 200 receiving Placebo and routine childhood vaccines.

7 General Considerations

7.1 Analysis Sets

For the purposes of analysis, the subject analysis sets are defined in **Table 3**.

Table 3: Subject Analysis Sets

Subject Analysis Set	Description
Enrolled analysis set	
• All subjects who signed the informed consent
Randomized analysis set	
• All subjects in the enrolled analysis set that were randomized
Immunogenicity evaluable analysis set	
• All subjects in the randomized analysis set that receive all doses of all study vaccines (routine and trial vaccines) within the required time window*
Immunogenicity full analysis set	
• All subjects in the randomized analysis set that receive at least one dose of a trial vaccine within the required time window*
Safety analysis set	
• All subjects in the randomized analysis set who are exposed to the trial vaccine. Subjects will be included in the analyses according to the trial vaccine (HIL-214 or Placebo) they actually received

*This window will be defined at the blinded data review meeting (BDRM)

7.2 Data Point Sets

The data point sets (DPS) are defined in **Table 4** and will be used to evaluate the estimands defined in the protocol.

Table 4: Data Point Sets

Data Point Sets	Description
Data point analysis set 1 (DPS1): Used for the primary immunogenicity estimands and for the secondary immunogenicity estimands	
• Immunogenicity evaluable analysis set• For subjects who receive a concomitant medication or other vaccine all data will be included
Data point analysis set 2 (DPS2): Used for the supplementary immunogenicity estimands	
• Immunogenicity full analysis set• For subjects who receive a vaccine outside of the required time window*, all data will be included• For subjects who receive a concomitant medication or other vaccine all data will be included
Data point analysis set 3 (DPS3): Used for the analysis of Safety data	
• Safety Analysis Set• For subjects who receive a vaccine outside of the required time window*, all data will be included• For subjects who received a concomitant medication or other vaccine all data will be included

*This window will be defined at the blinded data review meeting (BDRM)

7.3 Covariates

For the ANOVA models where only an overall analysis is presented, country will be included as a covariate.

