13.1.2 Immunogenicity Analysis

Immunogenicity data will be summarized by trial arm, for each licensed vaccine and corresponding immunogenicity assay, at all relevant time points, using:

- GMTs or GMCs and GMFR (as applicable) with 95% confidence interval (CI), geometric standard deviation (GSD), and minimum and maximum values, and
- Count and percentage of subjects with antibody titers/concentrations over pre-defined threshold, count and percentage of subjects achieving seroresponse to HIL-214, and 95% CIs for the percentages, computed using exact Clopper-Pearson method [17].

Assessment of primary objective:

The primary immunogenicity objective will be assessed using 95% CIs for differences in proportion of subjects with antibody concentrations/titers above a pre-specified threshold, computed by the Miettinen and Nurminen method [18], and 95% CIs for the geometric mean ratios, computed using the analysis of variance (ANOVA) model with natural logarithm of antibody titer/concentration as the response variable and trial arm as factor. Analyses will be done by licensed vaccine; for those vaccines used in more than one country, analyses will be repeated by country.

To address non-compliance with the vaccine administration schedule, a hypothetical strategy will be used under the assumption that lack of compliance is not related to the immune response to the routine pediatric vaccines and therefore, that infants who were not compliant with the vaccination schedule do not differ from the infants who did comply with regard to their immune response measurements. Hence, the primary immunogenicity analysis will be based on infants who were compliant with the vaccine administration schedule (i.e. received all doses of routine

CONFIDENTIAL

vaccines and trial vaccine within the allowed windows). According to the treatment policy strategy, blood sample results obtained after use of concomitant medications or other vaccines will be included in the analysis. Handling of missing data resulting from missing blood draws, non-evaluable samples (not enough volume), and blood draws outside the window will be described in the SAP.

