7.4 Subgroups

Table 5 shows the routine vaccines used in each country.

Table 5: Routine Vaccines Used in Each Country

Disease(s)	Routine Vaccine	
	Panama	USA (and Puerto Rico)
DTaP-Hib-IPV-HepB	Infanrix Hexa	Vaxelis
PCV13	Prevnar 13	Prevnar 13
RV1	Rotarix	Rotarix

Since the routine vaccines used in Panama and the USA to protect against rotavirus and the pneumococcus are the same, presenting an overall summary for the endpoints related to these vaccines is planned. Analysis of the immunogenicity endpoints for rotavirus and pneumococcal vaccines will be presented both overall and by country.

As the hexavalent vaccines used will be different in Panama and the USA there is no plan to provide an overall summary for immunogenicity endpoints related to antigens contained in these vaccines.

Therefore, analysis of all immunogenicity endpoints related to the hexavalent vaccines will be presented by country only.

The following subgroups will be presented:

- Country:
 - Panama
 - USA

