For continuous variables the ANOVA models will include all non-missing data for the parameter of interest and then the weights to account for the missing data. For binary data the proportions, which will be calculated on the complete cases data, will be reweighted, and the reweighted proportions will be used in the calculation of the confidence intervals. Therefore, in Equation (1) in [Section 5.4.1](#) will be calculated as the following:

$$\text{Difference in percentage} = (p_2 - p_1) * 100 = \left(\frac{(E_3|t_3 \times w_3) + (E_4|t_4 \times w_4)}{N_2} - \frac{(E_1|t_1 \times w_1) + (E_2|t_2 \times w_2)}{N_1} \right) * 100$$

Where E_i are the number of observed events in each category t_i and N_1 and N_2 are the number of subjects in the analysis set in the placebo and vaccine groups respectively. If all observed cases are positive in both vaccine groups, then the difference will be set to 0.

Equation (2) in [Section 5.4.1](#) will be calculated as the following:

$$\text{MN CI} = \left((\hat{p}_2 - \hat{p}_1) \pm Z_{1-\frac{\alpha}{2}} \sqrt{\lambda \left(\frac{\tilde{p}_2(1-\tilde{p}_2)}{N_2} + \frac{\tilde{p}_1(1-\tilde{p}_1)}{N_1} \right)} \right) * 100$$

Where $\lambda = \frac{N_1+N_2}{N_1+N_2-1}$.

If all observed cases are positive in both vaccine groups confidence intervals will not be calculated.

In the tables the number of events will be rounded to the nearest integer value and Clopper-Pearson CIs will be calculated using the exact weight-adjusted values using the Beta distribution. If all observed cases are positive the number of events will be set to N_1 and N_2 and these values will be used to calculate the confidence intervals.

If insufficient non-missing data are collected in participants with 1 trial vaccination the vaccine groups will be pooled to give the following vaccine options:

- Placebo vaccinations only (t_1)
- At least one HIL-214 vaccination (t_2)

The above formulae will be adjusted accordingly.

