9.1.1.3 Analysis Methods

A primary immunogenicity estimand and a supplementary estimand will be created for all of the endpoints outlined in **Table 8**. Analyses will be completed for the subgroups defined in **Section 7.4**.

For the primary immunogenicity estimands a complete case analysis will be performed, meaning any subjects with missing data for the parameter of interest will be excluded from the analysis.

For the supplementary immunogenicity estimands for the primary endpoints the missing data will be accounted for by reweighting the estimates using the method of inverse probability weighting. See **Section 7.5.1** for more details.

For the binary primary immunogenicity endpoints a standard summary for the categorical outcome will be presented as well as descriptive statistics for the continuous values. Further, the difference in percentage of subjects in the vaccine group with the event and the percentage of subjects in the

placebo group with the event will be evaluated. This will be presented along with a 95% CI calculated using the Miettinen and Nurminen [2] method as shown in **Section 5.4.1**.

For all continuous primary immunogenicity endpoints the geometric mean titer/concentration (GMT/GMC) with 95% CIs and geometric standard deviation (GSD) will be calculated. The GMRs between the vaccine group and the placebo group along with a 95% CI will be calculated using the analysis of variance (ANOVA) model with natural logarithm of antibody titer/concentration as the response variable and trial arm as a factor. Where country is used as a covariate (see **Section 7.3**) the adjusted GMs will also be presented. Further details can be found in **Section 5.4.3**.

For all primary immunogenicity parameters a reverse cumulative distribution curve will be produced, with titer/concentration on the x-axis and the percentage of patients below the titer value on the y-axis. All graphs will contain the two vaccine groups which will be overlaid.

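### The SAP's rule for adding country to the ANOVA fits none of the planned models, so it is not settled whether the overall PCV13 and RV1 geometric mean ratios are adjusted for the stratification factor

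*SAP*

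**What the plan says.** SAP 7.3 has one rule: "For the ANOVA models where only an overall analysis is presented, country will be included as a covariate".

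What is presented, and at what level, is set elsewhere:

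- SAP 7.4, rotavirus and pneumococcal vaccines: "Analysis of the immunogenicity endpoints for rotavirus and pneumococcal vaccines will be presented both overall and by country". The forest plots in SAP 9.1.1.3 follow the same pattern.
- SAP 7.4, hexavalent vaccines, which carry the three pertussis GMRs: "analysis of all immunogenicity endpoints related to the hexavalent vaccines will be presented by country only".
- SAP 9.2.1.3, norovirus HBGA-blocking titers: the two country subgroups only, HIL-214 recipients only, with no GMR between arms.

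On the model itself, Protocol 13.1.2 specifies an ANOVA with "natural logarithm of antibody titer/concentration as the response variable and trial arm as factor". SAP 9.1.1.3 repeats this: "natural logarithm of antibody titer/concentration as the response variable and trial arm as a factor". It then adds that, where country is a covariate under 7.3, "the adjusted GMs will also be presented". SAP 5.4.3 says that the GMR comes from an ANOVA but names no factors. For the supplementary estimands, SAP 7.5.1 says: "For continuous variables the ANOVA models will include all non-missing data for the parameter of interest and then the weights"; it names no factors either.

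Randomization is stratified by country (Protocol 8.6; SAP 5.2 and 7.7). SAP 13 lists two changes from the protocol, the hepatitis B assay and the principal stratum strategy. A country term is not among them.

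**The concern.** A pooled analysis of a trial stratified by country should say whether country is in the model. Here the rule that should say so describes an empty set of models, and the other passages point both ways. An arm-only model is supported by the literal 7.3, by the protocol, and by the only factor named in SAP 9.1.1.3. An adjusted model is supported by the sentence on adjusted geometric means, which would otherwise have nothing to refer to.

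At stake is the overall GMR and its 95% CI for the 13 PCV13 serotypes and RV1 IgA, under both the primary and the supplementary estimand. Omitting country leaves between-country variance in the residual, which widens the interval. If exclusions make the country mix differ between arms, it also moves the estimate. Protocol 13.1 has the SAP finalized before unblinding, so the model should be fixed in its wording.

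A lesser inconsistency sits in SAP 9.2.1.3. It confines the HBGA analysis to HIL-214 recipients but plans two-arm distribution curves, titer plots by vaccine group and placebo seroresponse bars with 95% CIs. Its own sentence on adjusted geometric means cannot apply to analyses done within country.

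**Working it through.** **Step 1. Test each planned ANOVA against the 7.3 condition.**

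| Endpoints | Number | Presented | Overall only? |
|---|---|---|---|
| FHA, PRN, PTX | 3 | by country only | no |
| PCV13 serotypes | 13 | overall and by country | no |
| RV1 IgA | 1 | overall and by country | no |
| HBGA GI.1, GII.4 | no between-arm GMR | by country only | no |

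The safety section plans no ANOVA. Models meeting the condition: 0.

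**Step 2. Count what is affected.** Primary endpoints: 1 DT + 1 TT + 3 polio + 1 PRP + 1 HBsAg + 3 pertussis + 13 PCV13 + 1 RV1 = 24. Analysed overall: 13 + 1 = 14. With a primary and a supplementary estimand each, 14 × 2 = 28 overall GMRs.

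**Step 3. Size the difference between the two models.** The plan has no figure of its own to reproduce: the trial is descriptive and unpowered (Protocol 13.3; SAP 6).

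From the documents: 200 per arm; at least 100 US infants of about 400 (Protocol 4.2), that is, a US share *p* = 0.25 at the target; two-sided 95% CIs. Assumed, because the documents give neither: within-country SD of ln concentration from 0.8 to 1.4, and a between-country ratio *R* of geometric mean concentrations from 1 to 3. Also assumed: the same country split in both arms.

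SE ratio (unadjusted / adjusted) = √(1 + p(1−p)·(ln R)² / SD²)

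For SD 1.0 and R = 2: √(1 + 0.1875 × 0.4805) = √1.0901 = 1.044.

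Equivalent N = 400 / (SE ratio)². An unadjusted analysis of 400 infants has the precision of an adjusted analysis of this many:

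| R | SE ratio, SD 0.8 | SD 1.0 | SD 1.4 | Equivalent N (SD 0.8 / 1.0 / 1.4) |
|---|---|---|---|---|
| 1 | 1.000 | 1.000 | 1.000 | 400 / 400 / 400 |
| 1.5 | 1.024 | 1.015 | 1.008 | 382 / 388 / 394 |
| 2 | 1.068 | 1.044 | 1.023 | 351 / 367 / 382 |
| 3 | 1.163 | 1.107 | 1.056 | 296 / 326 / 359 |

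Expected 95% CI at a true GMR of 1 = exp(± t(0.975, 398) × SD × √(2/200) × SE ratio). For SD 1.0:

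- adjusted: 0.822-1.217
- unadjusted, R = 1.5: 0.819-1.221
- unadjusted, R = 2: 0.814-1.228
- unadjusted, R = 3: 0.804-1.243

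Simulation (20,000 trials per setting; 50 US and 150 Panama infants per arm; lognormal data; true GMR 1) gave coverage of the unadjusted interval of 94.9-95.2% (R = 1), 95.1-95.5% (R = 1.5), 95.7-96.4% (R = 2) and 96.3-97.8% (R = 3). The adjusted interval covered 94.9-95.2% throughout.

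**Step 4. Relax the assumptions.** The US target is a minimum. With a 50% US share and SD 0.8 to 1.2, the ratio of CI half-widths on the log scale is 1.01-1.03 (R = 1.5), 1.04-1.09 (R = 2) and 1.10-1.21 (R = 3).

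If the US share differs between arms by δ, the unadjusted GMR is multiplied or divided by R^δ. For δ = 0.05: 1.5^0.05 = 1.02 and 3^0.05 = 1.06.

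**The case against.** The strongest reply is that 7.3 has a misplaced *only* and means that country is added only in models presented overall. That reading gives effect both to 7.3 and to the sentence on adjusted geometric means, and it picks out exactly the 14 pooled PCV13 and RV1 endpoints. It is probably what was intended. The text does not say it, however, and the literal reading agrees with the protocol's arm-only model.

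It can also be said that the consequence is small, that the SD and country ratio are assumptions, and that a threefold country ratio has no basis in the documents. All of this is fair. The calculation gives a range, not a forecast, and at R = 1 the two standard errors are the same.

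Protocol 13.1 leaves methodological detail to the SAP, so recording the country term in SAP 13 can be seen as good practice rather than the repair of an error. The weighted ANOVA in 7.5.1 is not a separate defect, since settling 7.3 settles it; the count of 28 shows how far one ambiguity reaches. Finally, SAP 9 already summarises immunogenicity data by vaccine group, so the HBGA inconsistency is one of wording.

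What remains is that the model for the overall GMRs has to be inferred from passages that disagree.

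**Conclusion.** The concern holds. As written, SAP 7.3 adds country to no model, and the SAP does not otherwise settle whether the overall GMRs for 14 of 24 primary endpoints are adjusted for the stratification factor.

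The practical effect is modest. With a 25% US share, 200 per arm and an equal country split, the unadjusted standard error is larger by nothing if the countries have equal geometric means, and by up to 6.8% at a twofold and 16.3% at a threefold difference (within-country SD 0.8 to 1.4). A larger US share can raise this to about 21%.

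Under balance the unadjusted analysis is unbiased and its interval conservative. Balance is likely under stratified randomization but not guaranteed, because the primary analysis is restricted to schedule-compliant infants with complete data. By-country results are unaffected, and no decision rule depends on these intervals. The change is worth making because it costs almost nothing and brings the pooled analysis into line with the randomization. The HBGA wording in 9.2.1.3 is a minor addition.

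**What to change.** 1. Reword SAP 7.3, for example: *Every overall ANOVA (PCV13 serotypes and RV1 IgA, primary and supplementary estimands) includes trial arm and country as factors; by-country ANOVAs include trial arm only.* Name the same factors in SAP 5.4.3.
2. Add one line to SAP 13 recording country as an addition to the model in Protocol 13.1.2.
3. In SAP 9.2.1.3, state that the secondary estimands concern HIL-214 recipients and that placebo HBGA results are shown descriptively, as SAP 9 already allows. Delete the sentence on adjusted geometric means there. A pooled HBGA summary is optional.

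The cost is a few sentences of SAP text and one line in SAP 13. No new data, samples or visits are needed.

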7.4 Subgroups

Table 5 shows the routine vaccines used in each country.

Table 5: Routine Vaccines Used in Each Country

Disease(s)	Routine Vaccine	
	Panama	USA (and Puerto Rico)
DTaP-Hib-IPV-HepB	Infanrix Hexa	Vaxelis
PCV13	Prevnar 13	Prevnar 13
RV1	Rotarix	Rotarix

Since the routine vaccines used in Panama and the USA to protect against rotavirus and the pneumococcus are the same, presenting an overall summary for the endpoints related to these vaccines is planned. Analysis of the immunogenicity endpoints for rotavirus and pneumococcal vaccines will be presented both overall and by country.

As the hexavalent vaccines used will be different in Panama and the USA there is no plan to provide an overall summary for immunogenicity endpoints related to antigens contained in these vaccines.

Therefore, analysis of all immunogenicity endpoints related to the hexavalent vaccines will be presented by country only.

The following subgroups will be presented:

- Country:
 - Panama
 - USA

7.5 Missing Data

7.5.1 Immunogenicity data

The reasons for having missing immunogenicity data are as follows:

- Study withdrawal prior to the blood draw (Visit 4)
- Non-evaluable samples, which may be as a result of a low volume of blood
- Blood draw outside of the permitted time window

For the primary and secondary immunogenicity estimands a principal stratum approach will be taken for the missing data. Therefore, a complete case (CC) analysis will be performed for these estimands based on the assumption that the data are missing completely at random. Immunogenicity results are not

expected to have any relationship with subject withdrawal from the study. Non-evaluable samples are expected to occur as a result of an issue with sample collection, storage, transportation, or analytical error and not due to the trial vaccine received. Blood draws outside of the permitted time window are expected to occur due to a planning or logistical error and won't be impacted by the trial vaccine received.

For the supplementary immunogenicity estimands a treatment policy approach will be applied to the missing data, using the assumption that any missing data would have been similar in subjects who had the same type of, and number of, trial vaccinations.

There are 4 different trial vaccine options that will be considered, they are:

- 1 placebo vaccination (t_1)
- 2 placebo vaccinations (t_2)
- 1 HIL-214 vaccination (t_3)
- 2 HIL-214 vaccinations (t_4)

To account for the missing data in this setting, inverse probability weighting [3] will be used. For this method, weights, relating to the probability of a subject having CC data, will be calculated for each of the 4 different trial vaccine options. A logistic regression model will be used to calculate the probability of having CC data, with one covariate that has 4 levels for the type of vaccine and the number of doses received.

The weights will be calculated in the following way:

$$w_i = \frac{1}{P(CC|\mathbf{t}_i)}$$

where \mathbf{t}_i describes the trial vaccine option the subject receives, as defined above.

For continuous variables the ANOVA models will include all non-missing data for the parameter of interest and then the weights to account for the missing data. For binary data the proportions, which will be calculated on the complete cases data, will be reweighted, and the reweighted proportions will be used in the calculation of the confidence intervals. Therefore, in Equation (1) in [Section 5.4.1](#) will be calculated as the following:

$$\text{Difference in percentage} = (p_2 - p_1) * 100 = \left(\frac{(E_3|t_3 \times w_3) + (E_4|t_4 \times w_4)}{N_2} - \frac{(E_1|t_1 \times w_1) + (E_2|t_2 \times w_2)}{N_1} \right) * 100$$

Where E_i are the number of observed events in each category t_i and N_1 and N_2 are the number of subjects in the analysis set in the placebo and vaccine groups respectively. If all observed cases are positive in both vaccine groups, then the difference will be set to 0.

Equation (2) in [Section 5.4.1](#) will be calculated as the following:

$$\text{MN CI} = \left((\hat{p}_2 - \hat{p}_1) \pm Z_{1-\frac{\alpha}{2}} \sqrt{\lambda \left(\frac{\tilde{p}_2(1-\tilde{p}_2)}{N_2} + \frac{\tilde{p}_1(1-\tilde{p}_1)}{N_1} \right)} \right) * 100$$

Where $\lambda = \frac{N_1+N_2}{N_1+N_2-1}$.

If all observed cases are positive in both vaccine groups confidence intervals will not be calculated.

In the tables the number of events will be rounded to the nearest integer value and Clopper-Pearson CIs will be calculated using the exact weight-adjusted values using the Beta distribution. If all observed cases are positive the number of events will be set to N_1 and N_2 and these values will be used to calculate the confidence intervals.

If insufficient non-missing data are collected in participants with 1 trial vaccination the vaccine groups will be pooled to give the following vaccine options:

- Placebo vaccinations only (t_1)
- At least one HIL-214 vaccination (t_2)

The above formulae will be adjusted accordingly.

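### If the supplementary inverse-probability weights are fitted on both countries together, which SAP 7.5.1 allows, by-country percentages are mis-scaled and can exceed 100%

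*SAP*

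**What the plan says.** SAP 7.5.1 covers missing Visit 4 results in the supplementary immunogenicity estimands "using the assumption that any missing data would have been similar in subjects who had the same type of, and number of, trial vaccinations". Weights "will be calculated for each of the 4 different trial vaccine options": one or two doses, of placebo or HIL-214. The model is stated in one sentence: "A logistic regression model will be used to calculate the probability of having CC data, with one covariate that has 4 levels". Each weight is the inverse of the fitted probability.

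For binary endpoints, weighted events are divided by N1 (placebo) or N2 (HIL-214), where "N_1 and N_2 are the number of subjects in the analysis set in the placebo and vaccine groups respectively". Two special rules apply. "If all observed cases are positive in both vaccine groups, then the difference will be set to 0", and where all observed cases are positive, the event counts are set to N1 and N2 for the Clopper-Pearson limits.

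On the level of reporting, SAP 7.4 says: "Therefore, analysis of all immunogenicity endpoints related to the hexavalent vaccines will be presented by country only". In SAP Table 8 the binary primary endpoints are DT, TT, polio types 1, 2 and 3, PRP and HBsAg. All 7 belong to the hexavalent vaccines. SAP 9.1.1.3, which introduces the primary and supplementary estimands together, adds: "Analyses will be completed for the subgroups defined in" Section 7.4, that is, Panama and the USA.

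**The concern.** Dividing a weighted count by N is valid only if the weights of the infants with a result sum to N in the group being reported. SAP 7.5.1 describes one model without country and puts no country index on the weights, the events or N. For the binary primary endpoints, however, the formula is only ever used within a country. A programmer who fits the model once on all infants and then tabulates by country has followed the text. That programmer would get percentages that are too high in the country with better completeness and too low in the other.

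The supplementary estimand is the plan's only alternative to a complete-case primary analysis that assumes data missing completely at random. If it can print a percentage above 100%, or an arm difference created by the pattern of missing samples, it is not a usable comparison.

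**Working it through.** The documents give no completeness rates and no reweighted percentages, so there is no planned figure to reproduce. The check is of the formula.

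**Inputs**
- 200 infants per arm (SAP 6); randomization stratified by country (SAP 5.2).
- Target of at least 100 US infants (protocol 4.2), so about 50 per arm at the minimum. Assumed split per arm: 150 Panama, 50 US.
- Assumed: all infants have two doses. Completeness and response rates are illustrative.

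**1. Does dividing by N work where the model is fitted?** Yes. With a single factor, the weight in cell i is n_i/c_i (infants / infants with a result). Over infants with a result, the weights sum to Σ c_i × n_i/c_i = N, provided that every occupied cell has at least one result. With mixed one-dose and two-dose cells, a numerical fit gave 200.0 of 200 per arm when pooled, and 150.0 and 50.0 when fitted within country.

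**2. Pooled weights, country tabulation.** For one vaccine option:

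reported % = observed % × (country completeness / pooled completeness)

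With results in 143/150 and 40/50, w = 200/183 = 1.0929.
- Panama, 141/143 positive (98.6%): 141 × 1.0929 = 154.1; 154.1/150 = 102.7%.
- US, 39/40 positive (97.5%): 39 × 1.0929 = 42.6; 42.6/50 = 85.2%.

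**3. Range (150/50 split)**

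| Completeness Panama/US | Pooled | Factor Panama | Factor US | Panama exceeds 100% if observed rate is above |
|---|---|---|---|---|
| 90/90 | 0.900 | 1.000 | 1.000 | never |
| 97/90 | 0.9525 | 1.018 | 0.945 | 98.2% |
| 92/84 | 0.900 | 1.022 | 0.933 | 97.8% |
| 94/80 | 0.905 | 1.039 | 0.884 | 96.3% |
| 95/75 | 0.900 | 1.056 | 0.833 | 94.7% |

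**4. Confidence limits.** At a weighted count of 154.1 of 150, N − x = −4.1, so the Clopper-Pearson Beta limits are undefined. The Miettinen-Nurminen (MN) formula as written in the SAP uses the estimate under no difference, a common rate, so it fails only if that rate exceeds 1. With 154.1/150 in one arm and 143/150 in the other, the common rate is 297.1/300 = 0.990 and the formula still evaluates.

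**5. Arm difference**
- Same country pattern in both arms: the difference is multiplied by the country factor. Zero stays zero. A 2-point difference becomes 2.1 in Panama (factor 0.9533/0.915 = 1.042) or 1.7 in the US (0.80/0.915 = 0.874).
- Pattern differs by arm: Panama 143/150 in both arms; US 38/50 (HIL-214) and 42/50 (placebo); response 98% throughout. The weights are 200/181 = 1.1050 and 200/185 = 1.0811.
  - US: 38 × 0.98 × 1.1050/50 = 82.3% v 42 × 0.98 × 1.0811/50 = 89.0%, a difference of −6.7 points where the truth is 0.
  - Panama: 140.14 × 1.1050 = 154.9 and 140.14 × 1.0811 = 151.5, both of 150. The common rate is 306.4/300 = 1.021, so here the MN variance term is also negative.

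**6. Special rules.** The all-positive rules act only when every observed result is positive. A rate of 98% or 99% is not caught, and the rule for the difference needs both arms to be all positive.

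**The case against.** The strongest reply is that the error needs a mixed reading: events and N taken by country, weights taken pooled. SAP 9.1.1.3 sends the whole analysis to the country subgroups. Since no overall hexavalent summary is planned, repeating the weight model within country is a natural reading. Under it the weights sum to N and nothing is wrong. This stands, and it is why the point is conditional. What remains is that SAP 7.5.1 neither requires that reading nor rules out the other, and the two give different results.

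A reader might infer more in three places.
- **That the supplementary percentages are wrong as the plan stands.** The documents do not support this. A pooled fit is permitted, not stated, and equal completeness across countries removes the error even then.
- **That no interval can be computed once a percentage exceeds 100%.** This is true of Clopper-Pearson. The MN formula fails only when the common rate exceeds 1.
- **That the trial's comparison of routine vaccines is compromised.** The primary analysis is unweighted complete case, the trial is descriptive, and the arm difference survives largely intact if missingness has the same country pattern in both arms. SAP 7.5.1 expects missing samples to be logistical and unrelated to trial vaccine, although chance alone can produce an imbalance with about 50 infants per arm.

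It is also fair that the supplementary estimand changes the analysis set and the intercurrent-event strategy, so it is not purely a check on missing data. SAP 9.1.1.3 ties completeness to the parameter of interest for the primary analysis. SAP 7.5.1 does not repeat this for the weights.

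**Conclusion.** The point holds conditionally. If the four-level model is fitted on both countries pooled and completeness differs by country, each by-country supplementary percentage is off by roughly the ratio of country to pooled completeness. Under the assumed patterns with unequal completeness in the table, that is a factor of 1.018 to 1.056 in Panama and 0.833 to 0.945 in the US. For endpoints with observed rates near 98%, several of these patterns give more than 100%. A material false arm difference arises mainly when the pattern also differs by arm; the −6.7 points in the US is one illustration. The 150/50 split, completeness and response rates are all assumptions.

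The scope is the supplementary analysis of the 7 binary primary endpoints. It extends to the supplementary seroresponse rates, also by country only (SAP 9.2.1.3), if the same formula is used. The weighted ANOVA ratios do not divide by N and do not share this problem. This is a should-fix for the supplementary estimands, not a must-fix for the trial.

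**What to change.** In SAP 7.5.1:
1. Fit the probability of a complete case within each country (country by vaccine option), for the parameter being analysed. Country as a main effect only does not guarantee that the weights sum to N in each country.
2. Define N1 and N2 by country.
3. Divide weighted events by the sum of the weights of infants with a result. After step 1 this agrees with dividing by N when every occupied cell has a result. In all cases it keeps the percentage between 0 and 100%, and it returns the complete-case value when weights are constant.
4. Apply the fallback that pools one-dose and two-dose infants by country, and state what counts as insufficient data.

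The cost is a few sentences and a programming loop over country and parameter, with no change to data or design. The small downside is that one-dose cells are sparser within a country, so the fallback will be used more often.
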